# 6.3. Primary Effectiveness Endpoint at 6 Months

The primary effectiveness endpoint at 6 months is defined as the effectiveness event-free rate at 6 months (183 days) post-procedure. If the analysis of the primary effectiveness endpoint at 6 months is not passed, then effectiveness may be re-evaluated via the primary effectiveness endpoint at 12 months, as described in Section 6.6.

Primary effectiveness events at 6 months are defined as:

- Acute procedural failure
  - Failure to achieve acute procedural success in the index procedure or in a repeat procedure during the blanking period.
  - Acute procedural success is defined as the achievement of electrical isolation of all PVs using the StablePoint catheter only. Electrical isolation of a PV is demonstrated by entrance block after 20 minutes waiting period. If exit block testing is performed, the PV will only be considered as isolated if both entrance and exit block testing are successful.

- Use of amiodarone post index procedure
- Use of non-study ablation catheter in the index procedure or in a repeat procedure during the blanking period
- More than one repeat procedure during the blanking period (90 days post index procedure)
- Surgical ablation of Atrial Fibrillation (AF)/Atrial Tachycardia (AT)/Atrial Flutter (AFL) post index procedure
- Documented atrial fibrillation, or new onset of atrial flutter or atrial tachycardia between 91 days and 183 days post index procedure captured by one of the following methods:
  - > 30 seconds in duration recording from the study specific event monitor or Holter Monitor
  - ≥ 10 second 12-lead Electrocardiography (ECG)
- Any of the following interventions for atrial fibrillation, or new onset of atrial flutter or atrial tachycardia between 91 days and 183 days post index procedure:
  - Repeat procedure
  - Electrical and/or pharmacological cardioversion
  - Prescribed any AAD\*
- \*AADs for endpoint will consist of all Class I/III, including Amiodarone, and any Class II/IV medications taken for control of atrial fibrillation (AF)/Atrial tachycardia (AT)/Atrial flutter (AFL) recurrence.

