# 6.5. Primary Effectiveness Endpoint at 12 Months

The primary effectiveness endpoint at 12 months is defined as the event-free rate at 12 months (365 days) post-procedure.

Primary effectiveness events at 12 months are defined as:

- Acute procedural failure
  - Failure to achieve acute procedural success in the index procedure or in a repeat procedure during the blanking period.
  - Acute procedural success is defined as the achievement of electrical isolation of all PVs using the StablePoint catheter only. Electrical isolation of a PV is demonstrated by entrance block after 20 minutes waiting period. If exit block testing is performed, the PV will only be considered as isolated if both entrance and exit block testing are successful.
- Use of amiodarone post index procedure
- Use of non-study ablation catheter in the index procedure or in a repeat procedure during the blanking period.
- More than one repeat procedure during the blanking period (90 days post index procedure)
- Surgical ablation of Atrial Fibrillation (AF)/Atrial Tachycardia (AT)/Atrial Flutter (AFL) post index procedure
- Documented atrial fibrillation, or new onset of atrial flutter or atrial tachycardia between 91 days and 365 days post index procedure captured by one of the following methods:
  - ≥ 30 seconds in duration from the study specific event monitor or Holter Monitor

- ≥ 10 second 12-lead Electrocardiography (ECG)
- Any of the following interventions for atrial fibrillation, or new onset of atrial flutter or atrial tachycardia between 91 days and 365 days post index procedure:
  - Repeat procedure
  - Electrical and/or pharmacological cardioversion
  - Prescribed any AAD\*

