# 6.7. Secondary Endpoints

Secondary Endpoints include the following:

- Secondary Safety Endpoint SAE and AE Rates
- Secondary Effectiveness Endpoint 1 New or Increased Dose of AAD
- Secondary Effectiveness Endpoint 2 Single Procedure Success defined as freedom from primary effectiveness failure without a repeat procedure
- Secondary Effectiveness Endpoint 3 Symptomatic Recurrence: freedom from documented symptomatic AF/AT/AFL recurrence

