Evaluate the effectiveness of the StablePoint Catheter, assessed initially at 6 months, with a potential evaluation at 12 months if the 6-month analysis is not passed.	Failure free rate including failure to achieve success at index or repeated procedure in blanking period, more than one repeated procedure during blanking period, documented AF/AT or new onset AFL or interventions to treat these arrhythmias after blanking period, including repeated procedures cardioversion or pharmacologic treatment.  Effectiveness will be evaluated at a sixmonth analysis. If the 6-month analysis is not passed, an additional evaluation of primary effectiveness will be done at twelve months.	The effectiveness endpoint and the performance goal at 12 months were established based on the recommendations available in the 2017 HRS expert consensus statement on catheter and surgical ablation of atrial fibrillation.  The expected rates for both the 6- and 12-month Primary Effectiveness endpoints was determined based on Boston Scientific's ZERO AF study data. The 6-month Primary Effectiveness endpoint performance goal was determined by the meta-analysis of pivotal and IDE studies on AF ablation (section 11.1.2.2)								

		Page 45 of 129				
Evaluate the 12-months safety of the StablePoint Catheter	The primary safety endpoint is defined as the safety event-free rate at 12 months post-procedure.	The list of events contributing to the primary safety endpoints was selected from those typically associate with catheter ablation of AF.				
Evaluate the 12-months effectiveness of the StablePoint Catheter	Failure free rate including failure to achieve success at index or repeated procedure in blanking period, more than one repeated procedure during blanking period, documented AF/AT or new onset AFL or interventions to treat these arrhythmias after blanking period, including repeated procedures cardioversion or pharmacologic treatment.	The effectiveness endpoint and the performance goal at 12 months were established based on the recommendations available in the 2017 HRS expert consensus statement on catheter and surgical ablation of atrial fibrillation.				
	Secondary Endpoin	ts				
Adverse events reporting	SAE and AE Rates	Complete overview of the safety events collected in the study				
Anti-arrhythmic treatment	New or Increased Dose of AAD	This is an analysis of a component of the primary effectiveness endpoint				

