# 10.4.1.3. AADs post blanking period

Investigators must stop administration of AADs for any atrial tachyarrhythmia after the blanking period on the date of the 3-Month Follow-Up. If the investigator determines that the subject must be prescribed any dose of AAD\* for treatment of any atrial tachyarrhythmia after the blanking period, the subject will be considered a Primary Effectiveness Failure.

\*AADs for endpoint will consist of all Class I/III and any Class II/IV medications taken for control of AF/AT/AFL recurrence.

Treatment with Class II/IV medications for conditions other than control of atrial arrhythmia recurrence is permitted and will be documented. Every effort should be made to keep those drugs at a stable dose over the entire course of the study.

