#### 10.6.2.7.2 Cavo-tricuspid Isthmus (CTI)

Ablation of the CTI may be completed for subjects with a history of Type I Atrial Flutter or those in which Type I Atrial Flutter occurs during the procedure (spontaneously or induced). If CTI ablation is performed, bidirectional block will be assessed and documented on the appropriate CRF. Point by point ablation is highly recommended and physicians must use the IntellaNav StablePoint Catheter to complete all ablations in accordance with the IFU and per the Ablation Technique section of this protocol.

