# 10.7. Additional/Repeat Procedure

One repeat ablation procedure for PAF is allowed within the blanking period only if considered medically necessary due to subject's intolerability of the PAF. An additional ablation procedure outside the blanking period is considered an effectiveness endpoint failure. The StablePoint Catheter System must be used for a repeat ablation procedure. In case an additional ablation procedure (including to but not limited to additional ablation procedures for PAF) occurs during the month 12 follow up period, the data of this procedure will be entered in the 'Additional Procedure' eCRF.

A repeat ablation procedure for PAF may be medically necessary in certain subjects after the index ablation procedure due to recurrences of PAF or other tachyarrhythmias requiring treatment. If a repeat ablation procedure is conducted, the Investigator must follow the

protocol as outlined in Sections 10.4 (Medications), 10.5 (General Study Information) and 10.6.2.1 through 10.6.2.6, which describes the initial 3D mapping, ablation technique, PVI validation, esophagus management and phrenic nerve assessment. After the repeat procedure, a neurology consult is only required if NIHSS scale worsens from the previous assessment. The NIHSS at Pre-Discharge must be performed Day 1 to 7 after the repeat procedure. All NIHSS assessments must be completed by a person certified in the administration of the NIHSS. Data collection requirements for the repeat procedure for PAF are the same as those for the Index Procedure for PAF.

If the StablePoint Catheter System is not used for a repeat procedure during the blanking period, it is considered a deviation and a study endpoint failure.

Subjects must follow the same anticoagulation requirements as defined for the index procedure in Section 10.4.2 prior to proceeding with the repeat ablation procedure for PAF.

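### A prior flutter or atrial tachycardia that returns and is treated after blanking with a non-amiodarone antiarrhythmic or a catheter ablation is event-free under 6.3/6.5 but a failure under 10.4.1.3 or 10.7

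*Combined protocol and SAP*

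**What the plan says.** Section 6.3 has two event items that depend on the arrhythmia. The first is a recording: "Documented atrial fibrillation, or new onset of atrial flutter or atrial tachycardia between 91 days and 183 days post index procedure". The second is treatment (repeat procedure, cardioversion or any AAD): "Any of the following interventions for atrial fibrillation, or new onset of atrial flutter or atrial tachycardia between 91 days and 183 days". Section 6.5 repeats both to day 365, the second as "Any of the following interventions for atrial fibrillation, or new onset of atrial flutter or atrial tachycardia between 91 days and 365 days". The synopsis and the Primary Effectiveness Failure entry in Table 26-2 use the same qualifier. Atrial fibrillation carries no such limit.

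Two other sections also say what counts as a failure. Section 10.4.1.3, on an AAD prescribed after blanking, reads "treatment of any atrial tachyarrhythmia after the blanking period, the subject will be considered a Primary Effectiveness Failure". Section 10.7 reads "An additional ablation procedure outside the blanking period is considered an effectiveness endpoint failure". Neither mentions new onset. The overview in Table 6-2 (section 6.8) words it a third way, with the qualifier on flutter only: "documented AF/AT or new onset AFL or interventions to treat these arrhythmias after blanking period".

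Subjects with prior flutter can be enrolled. It is not among the exclusion criteria, and section 10.6.2.7.2 provides that "Ablation of the CTI may be completed for subjects with a history of Type I Atrial Flutter".

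**The concern.** The capitalised term Primary Effectiveness Failure is defined in Table 26-2 with the new-onset limit and used in 10.4.1.3 without it. For some subjects the two uses give opposite outcomes. The trial has one arm, is open, and is judged against fixed performance goals. A choice of failure rule made after outcomes are known would therefore bear directly on the primary result, and there is no control arm in which it could cancel out.

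Nothing in the protocol settles what *new onset* means. Table 26-2 has no entry for it. Section 13.4.1 assigns rhythm determination and event adjudication, but does not ask anyone to compare the rhythm with the subject's baseline history.

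**Working it through.** **Step 1. The rules side by side.** Take a subject with documented flutter or atrial tachycardia before enrolment. It returns after day 90, within the endpoint window, with no atrial fibrillation and no other failure event. Read *new onset* as no prior history.

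| What happens | 6.3 / 6.5 | 10.4.1.3 | 10.7 | Conflict |
|---|---|---|---|---|
| Recorded, untreated | not counted | silent | silent | no |
| Electrical cardioversion only | not counted | silent | silent | no |
| Endpoint AAD other than amiodarone | not counted | failure | silent | **yes** |
| Additional catheter ablation | not counted | silent | failure | **yes** |
| Amiodarone | failure | failure | silent | no |
| Surgical ablation of AF/AT/AFL | failure | silent | at most failure | no |

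The last two rows agree because 6.3 and 6.5 list amiodarone and surgical ablation as separate events, whatever the history. Under the Table 6-2 wording, a returning atrial tachycardia would count even if untreated, and a returning flutter would not.

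**Step 2. The plan's own sample sizes.** Sections 11.1.3.2 and 11.1.5.2 give goals of 60% and 50%, expected rates of 72% and 60%, one-sided 2.5%, power 90% and attrition 10%.

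n = [(1.960·√(p0(1−p0)) + 1.282·√(p1(1−p1))) / (p1−p0)]²

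- 6 months: [(0.9602 + 0.5754)/0.12]² = 163.8, so 164; 164/0.9 = 182.2, so **183**, as stated.
- 12 months: [(0.9800 + 0.6278)/0.10]² = 258.5, so 259; 259/0.9 = 287.8, so **288**, as stated.

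**Step 3. Sensitivity to the rule.** Assume that the planning rates follow the new-onset rule and that the broader rule adds k points of failures. The documents supply neither fact. Power = Φ{[(p1−k−p0)√n − 1.960√(p0(1−p0))] / √((p1−k)(1−p1+k))}.

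| k (points) | 6 months, n = 164 | 12 months, n = 259 |
|---|---|---|
| 0 | 90% | 90% |
| 1 | 84% | 83% |
| 2 | 76% | 73% |
| 3 | 66% | 62% |
| 5 | 45% | 36% |

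One point is about 2 of 183 subjects or 3 of 288. Section 11.3.1 uses all available data, so more subjects will contribute. With 269 evaluable (299 × 0.9), 6-month power for k = 1, 2, 3 is 97%, 93% and 87%. That is an upper figure, because not all 299 need have reached 6 months by then.

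**Step 4. Distance to the pass mark.** Without censoring, S = 1 − d/n, SE = √(d/(n(n−d))) / |ln S|, and the log-log limit is S^exp(1.960·SE).

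- 12 months, n = 299: 132 events give 50.03% (pass) and 133 give 49.70% (fail). At the planned 60%, 0.40 × 299 ≈ 120 events, so 12 switches still pass and 13 do not.
- 6 months, n = 183: 59 events give 60.46% (pass) and 60 give 59.90% (fail). At the planned 72%, 0.28 × 183 ≈ 51 events, so 8 switches still pass and 9 do not.

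**Step 5. How many could switch.** The documents give no prevalence of prior flutter or tachycardia. As an assumption only: 10–30% with such a history, and 5–20% of those with a return after day 90 and no other failure, give 299 × 0.10 × 0.05 = 1.5 up to 299 × 0.30 × 0.20 = 17.9 subjects. This counts every return, including the untreated and cardioversion-only cases that Step 1 shows are not in conflict. The number in conflict would be smaller.

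**The case against.** The best defence is that the analyst does have a pointer. Sections 11.1.3 and 11.1.5 define the endpoints by reference to 6.3 and 6.5. The new-onset wording appears in seven places (synopsis, 6.3, 6.5, 11.2.2, 11.2.3, 11.2.4 and Table 26-2), which suggests intent. Sections 10.4.1.3 and 10.7 are medication and procedure instructions, and Table 6-2 is an incomplete overview. This stands as a reason to expect that 6.3 and 6.5 would prevail. It does not remove the conflict, because 10.4.1.3 uses the defined endpoint term itself and sites will read it as the rule.

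*New onset* could also mean onset within the window, which would dissolve most of the conflict. That reading is possible. It is less natural, because the qualifier is withheld from atrial fibrillation, the arrhythmia every subject already has. Either way a definition is needed.

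A reader might infer three stronger things that the documents do not support:

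- That any returning flutter is both success and failure. Step 1 limits the conflict to two treatments. Section 10.7 reaches its result by counting every later ablation, not by naming any atrial tachyarrhythmia.
- That the secondary endpoints share the contradiction. Section 10.4.1.3 speaks only of the primary endpoint, and section 11.2 calls the secondary endpoints exploratory. Secondary Endpoint 3 is labelled "freedom from documented symptomatic AF/AT/AFL recurrence" while 11.2.4 lists new-onset flutter and tachycardia; that is a wording mismatch of less weight.
- That *new onset* must be deleted. Keeping it, defining it and amending the other sections would equally cure the conflict. The expected rates come from ZERO AF data and the 6-month goal from a meta-analysis of study-defined rates, and the documents do not show whether those counted recurring flutter. Broadening the rule could break comparability with the goal.

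**Conclusion.** Wrong as written. The protocol holds two incompatible failure rules for its primary effectiveness endpoint, at 6 and at 12 months. They collide for subjects with prior flutter or atrial tachycardia whose arrhythmia returns and is treated after blanking with a non-amiodarone AAD or an additional catheter ablation. This rests on reading *new onset* as no prior history, which is the natural reading but is not stated.

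The size is unknown. At the planned rates, with no censoring, about 9 switches among 183 subjects at 6 months or 13 among 299 at 12 months would turn a pass into a fail. Fewer would matter if the observed rate were closer to the goal. Most of the assumed range in Step 5 would not reverse a result that lands at the planned 12-month rate. A reader might conclude that 6.3 and 6.5 inflate the event-free rate; the documents do not support that without knowing which definition lies behind the goals.

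**What to change.** Before the 6-month analysis:

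1. Reconcile the synopsis, 6.3, 6.5, Table 6-2, 10.4.1.3, 10.7 and Table 26-2 to one primary-endpoint rule. This review does not say which.
2. If *new onset* is kept, define it and say who classifies it, for example against the arrhythmia history already collected at baseline (10.6.1).
3. Prespecify the primary endpoint under the other rule as a sensitivity analysis at both 6 and 12 months.
4. Check the chosen rule against the definitions behind the ZERO AF expected rates and the meta-analysis goal, and state the result.
5. Leave the symptomatic-only restriction in 11.2.4 and the new-or-increased-dose restriction in 11.2.2 intact, since they define those endpoints.

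The cost is an amendment to wording and a little more analysis. The recordings and baseline history are already collected. If the broader rule is chosen, the event-free rate will be lower and some power is lost, on the scale shown in Step 3.

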# 6.4. Primary Safety Endpoint at 12 Months

The primary safety endpoint at 12 months is defined as the safety event-free rate at 12 months post-procedure.

Primary safety events will consist of a composite of the following serious procedure-related and/or device-related adverse events.

The following events will be counted through 7 days post index procedure or hospital discharge, whichever is later:

- Death
- Myocardial infarction (MI)
- Vagal Nerve Injury/Gastroparesis
- Transient ischemic attack (TIA)
- Stroke/Cerebrovascular accident (CVA)
- Thromboembolism
- Pericarditis
- Pneumothorax
- Major vascular access complications
- Pulmonary edema/heart failure

AV block\*

The following events will be counted through 30 days post index procedure:

Cardiac tamponade/perforation

And the following events will be counted through 12 months post index procedure:

- Atrial esophageal fistula
- Severe pulmonary vein stenosis (≥70% reduction in the diameter of the PV or PV branch from baseline)
- Persistent phrenic nerve palsy\*\*
- \* AV block not attributable to medication effect or vasovagal reaction.
- \*\*A non-recovered phrenic nerve palsy at 12 months post index procedure will count as a chronic primary endpoint. The study will collect information on phrenic nerve palsy observed before the end of the index procedure and, in case it occurred, will track information for potential recovery during the study visits.

# 6.5. Primary Effectiveness Endpoint at 12 Months

The primary effectiveness endpoint at 12 months is defined as the event-free rate at 12 months (365 days) post-procedure.

Primary effectiveness events at 12 months are defined as:

- Acute procedural failure
  - Failure to achieve acute procedural success in the index procedure or in a repeat procedure during the blanking period.
  - Acute procedural success is defined as the achievement of electrical isolation of all PVs using the StablePoint catheter only. Electrical isolation of a PV is demonstrated by entrance block after 20 minutes waiting period. If exit block testing is performed, the PV will only be considered as isolated if both entrance and exit block testing are successful.
- Use of amiodarone post index procedure
- Use of non-study ablation catheter in the index procedure or in a repeat procedure during the blanking period.
- More than one repeat procedure during the blanking period (90 days post index procedure)
- Surgical ablation of Atrial Fibrillation (AF)/Atrial Tachycardia (AT)/Atrial Flutter (AFL) post index procedure
- Documented atrial fibrillation, or new onset of atrial flutter or atrial tachycardia between 91 days and 365 days post index procedure captured by one of the following methods:
  - ≥ 30 seconds in duration from the study specific event monitor or Holter Monitor

- ≥ 10 second 12-lead Electrocardiography (ECG)
- Any of the following interventions for atrial fibrillation, or new onset of atrial flutter or atrial tachycardia between 91 days and 365 days post index procedure:
  - Repeat procedure
  - Electrical and/or pharmacological cardioversion
  - Prescribed any AAD\*

# 6.6. Study Success Criteria

Two sets of study success criteria are defined for the study. These are Study Success for PMA Submission and Overall Study success. Study Success for PMA Submission refers to the criteria that must be met prior to sPMA submission and can potentially be achieved at the time of the 6-month analysis. If Study Success for PMA Submission is not achieved at the 6month analysis, then it may be re-assessed at 12 months. Overall Study Success refers to the success criteria assessed only after 12-month follow-up is complete. Type-I error control across all endpoint assessments is discussed in Section 11.3.2.2.

# 6.6.1. Study Success for PMA Submission

Either of the following cases must occur to achieve study success for PMA submission:

- Study Success for PMA Submission Case 1 (all must occur):
  - Primary safety endpoint at 30 days is met.
  - Primary effectiveness endpoint acute procedural success is met.
  - Primary effectiveness endpoint at 6 months is met.

If the primary effectiveness endpoint at 6 months fails in Case 1 above, the primary effectiveness endpoint will be reassessed at 12 Months, as described below in Study Success for PMA Submission Case 2 and will be followed by the PMA submission at that time.

- Study Success for PMA Submission Case 2 (all must occur):
  - Primary safety endpoint at 30 days is met.
  - Primary effectiveness endpoint acute procedural success is met.
  - Primary effectiveness endpoint at 6 months is failed.
  - Primary effectiveness endpoint at 12 months is met.

\*AADs for endpoint will consist of all Class I/III, including Amiodarone, and any Class II/IV medications taken for control of atrial fibrillation (AF)/Atrial tachycardia (AT)/Atrial flutter (AFL) recurrence.

